2.2.2. Secondary evaluation criteria

- The severity of pressure ulcers will be assessed using the NPUAP scale

- The duration of catheter retention will be calculated between the time the catheter is inserted and the time it is removed.

- The presence of a nosocomial infection related to the peripheral venous catheter.

This will be defined by a peripheral venous catheter culture $>10^3$ CFU/ml, if the peripheral venous catheter is sent for culture due to suspected infection and in the absence of antibiotic treatment. In the presence of antibiotic treatment, it will be defined by the presence of pus and/or regression of infectious signs within 48 hours of removal of the peripheral venous catheter.

3. STUDY POPULATION

3.1. DESCRIPTION OF THE POPULATION

The study plans to include 396 patients with the aim of obtaining 360 randomised patients (see section 5.2.1 Description of planned statistical methods).

Inclusions will cease when the potential number of randomised patients has been reached.

Patients will be children aged between 1 month and 18 years, hospitalised in the General Paediatrics Department of the CHD Vendée hospital in La Roche-sur-Yon, or with a high probability of being hospitalised in Paediatrics following a visit to the Paediatric Emergency Department, for whom there is an indication for the insertion of a peripheral venous catheter.

We have chosen the age range of 1 month to 18 years because it appears that the skin is immature before 3-4 weeks of life and therefore at greater risk of iatrogenic skin lesions, according to the French Society of Dermatology (14).

As the patients are minors, prior authorisation will be sought from their parents.

3.2. INCLUSION CRITERIA

Patient:

- Aged between 1 month and 18 years, according to the admission criteria of the paediatric department of the CHD La Roche sur Yon.
- Hospitalised in paediatrics or attending the paediatric emergency department with a high probability of subsequent hospitalisation in paediatrics.
- With an indication for the insertion of a short peripheral venous catheter
- Written consent of the person(s) with parental authority

3.3. EXCLUSION CRITERIA

- Children with pre-existing skin conditions at the time of inclusion and at the puncture site (atopic dermatitis, skin infection, skin wound, chickenpox, epidermolysis bullosa)

- Allergy to fixation devices
- Known immunocompromised children
- Refusal of the patient or legal guardians to participate in the project
- Emergency life-saving treatment
- Patient already included in the study
- Patient without social security coverage

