2.1.2. Primary assessment criterion

The primary endpoint is the occurrence of pressure ulcers of grade ≥ 1 on the NPUAP scale at the catheter/extender junction. The assessment will be carried out blind by a childcare assistant from the department.

2.2. *SECONDARY OBJECTIVES AND EVALUATION CRITERIA*

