4. DESIGN AND CONDUCT OF THE STUDY

4.1. STUDY SCHEDULE

- Recruitment period: 48 months
- Duration of patient participation in the study: until catheter removal.

a) Inclusion

Information and verbal consent regarding participation in the study will be obtained from the minor patient. Consent will be signed by the person(s) with parental authority (see 7.6.1: special case of the presence of only one parent).

This will be done once the medical prescription for peripheral venous access has been issued, the inclusion and exclusion criteria have been verified, and before randomisation.

The patient will be:

- either in the paediatric emergency department;
- or already hospitalised in paediatrics;

A table tracking patients to whom the study has been proposed will be kept up to date, noting the reasons for non-inclusion and refusals to participate.

b) Randomisation

Once consent to participate has been obtained, randomisation will be carried out via the computerised data base (eCRF):

- VVP placement without compress group: reference strategy group.
- VVP placement with compress group: alternative strategy group.

The peripheral venous line will then be placed according to the group designated by randomisation.

Details of the procedure for each arm are described in 4.4.

c) Follow-up

In both groups, catheter management and maintenance will be carried out by the nursing team responsible for the patient in the paediatric ward in accordance with current institutional procedures (see Appendices 1 and 2, catheter placement protocol with and without compress).

Data will be collected at the time of PPV removal. The peripheral line placed is valuable. In practice, the lines are maintained until the end of treatment unless there is redness and/or discharge at the puncture site.

When the catheter is removed, the nurse in charge of the patient removes the crepe bandage, the compress if there is one, and the catheter.

A childcare assistant from the department who has not been caring for the patient will then be called to assess the condition of the skin and report on the appearance and grade of any bedsores. The nurse will also note the presence or absence of signs of infection according to the Maddox scale. If the index is greater than 3, the paediatrician will prescribe that the catheter be sent for culture.

The microbiological analysis will be carried out by the clinical research biology team at the CHD Vendée.

d) Study design

[figure not shown]

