Actions	D0 (Inclusion visit)	Every day	J Withdrawal from the VVP
Patient information	X		
Informed consent from the patient (verbal) + legal guardian (written)	X		
Randomisation	X		
Peripheral venous access	X		
Monitoring of puncture site (catheter sent for culture if local infection)		X	
Assessment of the presence of a lesion + severity of the lesion by a childcare assistant			X

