4.5. DESCRIPTION OF THE EVALUATION AND DATA COLLECTED

The primary endpoint is the development of a pressure ulcer of grade ≥ 1 on the NPUAP scale at the catheter/tubing junction.

This area is assessed several times a day by nurses, who remove the bandage without removing the fixation device (compress and transparent adhesive dressing). However, if the compress is soiled, the dressing will be changed.

NPUAP scale

The NPUAP pressure ulcer assessment scale, translated from English by ANAES, will be used. This scale allows pressure ulcers to be assessed according to four stages, graded from 1 to 4, with stage 1 being the least severe.

- Stage I: The first stage is an observable change in intact skin, related to pressure and manifested by a change in one or more of the following characteristics compared to the adjacent or contralateral body area: skin temperature (warm or cold), tissue consistency (firm or soft) and/or sensitivity (pain, itching). In people with fair skin, the pressure ulcer appears as persistent localised redness, while in people with pigmented skin, the pressure ulcer may be a persistent red, blue or purplish colour.

Example: Stage 1 pressure ulcer

- Stage II: Loss of part of the skin's thickness; this loss affects the epidermis, the dermis, or both. The pressure ulcer is superficial and clinically presents as an abrasion, blister, or shallow ulceration.

- Stage III: Loss of all skin thickness with alteration or necrosis of the subcutaneous tissue; this may extend to the fascia, but not beyond. The pressure ulcer appears clinically as a deep ulceration with or without invasion of surrounding tissues.
- Stage IV: Loss of the entire thickness of the skin with significant tissue destruction, or involvement of muscles, bones, or supporting structures (e.g., tendons, joints). Invasion and fistulas may be associated with stage IV pressure ulcers.

The catheter will be removed by the nurse in charge of the patient.

In order to allow for a blind assessment of the primary endpoint, this will be performed by a childcare assistant from the department who is on duty 24 hours a day and has not previously cared for the child. The childcare assistant will assess the pressure area and then note their observations in the patient's file (presence or absence of pressure ulcers and NPUAP grade, if applicable).

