5.2. STATISTICS

Responsible for statistical analysis:

[name]
Vendée Departmental Hospital Centre
Clinical Research Unit
[contact]

Software

The analyses will be performed using R software version 3.5.1

5.2.1. Description of planned statistical methods, including the schedule for planned interim analyses

All variables will be described globally and by group. The description will include the numbers and percentages of modalities for qualitative variables and the minimum, maximum, mean, standard deviation and median for quantitative variables.

Primary endpoint

The primary endpoint is defined as the presence of a pressure ulcer at the junction of the catheter with the extension tube or peripheral venous line tubing. The assessment will be performed upon catheter removal and blinded by a nursing assistant from the department.

The percentage of patients will be presented with a 95% confidence interval in the two groups and will be compared using a Chi-square test.

In a second step, the two groups will be compared using logistic regression to take into account the duration of catheter retention.

Secondary criteria

The severity of pressure ulcers will be described between the two groups. At each stage of the NPUAP scale, the number and percentage of patients will be presented. A Mann-Whitney test will be applied to compare the two groups.

The average duration of catheter retention will be described for the two groups with a 95% confidence interval. It will be compared using a Student's t-test.

The number of patients with nosocomial infection will be described in the two groups. No statistical test will be performed.

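### The skin exclusion names the puncture site but the primary outcome is read at the catheter/extension junction, with no baseline check of that skin in the schedule shown, so an earlier pressure-type mark can be counted as a new ulcer

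*Combined protocol and SAP*

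**What the plan says.** - **Exclusion (section 3.3).** It removes "Children with pre-existing skin conditions at the time of inclusion and at the puncture site". The examples given are diseases, infections and wounds: "at the puncture site (atopic dermatitis, skin infection, skin wound, chickenpox, epidermolysis bullosa"). The junction is not named in any eligibility criterion.
- **Primary endpoint (section 2.1.2).** "The primary endpoint is the occurrence of pressure ulcers of grade ≥ 1 on the NPUAP scale at the catheter/extender junction". The objective in section 2.1.1 is to compare incidence.
- **Endpoint as analysed (section 5.2.1).** "The primary endpoint is defined as the presence of a pressure ulcer at the junction of the catheter with the extension tube" or line tubing. There is no condition that the lesion was absent at insertion.
- **Schedule (section 4.1).** The row "Assessment of the presence of a lesion + severity of the lesion by a childcare assistant" is marked only in the removal column. The D0 entries are information, consent, randomisation and venous access. The daily row is monitoring of the puncture site.
- **Assessor (section 4.5).** The reading is "performed by a childcare assistant from the department who is on duty 24 hours a day and has not previously cared for the child".
- **Who can enter (sections 3.2, 3.3 and 4.1).** A child may be in the emergency department "or already hospitalised in paediatrics". Earlier inclusion in this study excludes a child; an earlier non-study line does not.
- **Order of events (section 4.1).** Criteria are verified, the child is randomised, and the line is then placed.

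**The concern.** An incidence endpoint needs skin known to be clear at the start, or a record of what was already there. Here the eligibility check protects one patch of skin and the outcome is read on a neighbouring one. An inpatient whose earlier line has failed could be enrolled and have the new junction placed on skin that already carries residual redness or an abrasion. The assessor is kept apart from the child's care to protect blinding, so has no knowledge of the skin at insertion unless it was written down.

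Two things are at stake. First, section 5.2.2 says the pilot is to give reliable data on these ulcers, and section 1.1 says those data may support a larger multicentre study. Counting old marks as new inflates the rate in both arms. Second, the contrast between arms is diluted. Section 1.1 reports that the department's junction lesions are mainly stage I, the grade most easily confused with earlier redness.

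**Working it through.** **Inputs.** From sections 5.2.1, 5.2.2 and 5.2.8: a 15-point difference, 80% power, 5% alpha, 346 patients, 360 to be randomised 1:1 (180 per arm), and a Chi-square test. Not given: the two rates, the sidedness of the test, and q, the share of children with a mark on the junction skin that would be graded at removal. These are assumed below.

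**Step 1: the plan's own figure.** Per-arm size, pooled variance, two-sided, no continuity correction:

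n = [1.96·√(2p̄(1 − p̄)) + 0.842·√(p₁(1 − p₁) + p₂(1 − p₂))]² / (p₁ − p₂)²

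With p₁ = 55%, p₂ = 40% and p̄ = 47.5%, n = 172.8, rounded up to 173, so 346 in total. The stated size reproduces exactly (60% and 45% give the same result). At 57.5% and 42.5%, the least favourable pair for a 15-point difference, the total is 348. The point made here does not affect this calculation.

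**Step 2: effect of marks counted as events.** If a share q in both arms is scored as an event whatever happens later:

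- Observed rate: p′ = q + (1 − q)p, a rise of q(1 − p).
- Observed difference: p₁′ − p₂′ = (1 − q)(p₁ − p₂).
- If p₁ = p₂, then p₁′ = p₂′, so the null hypothesis is preserved and the test keeps its nominal 5% level.

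**Step 3: power.** Exact enumeration of two binomials, 180 per arm, uncorrected Chi-square at two-sided 5%, true rates 57.5% and 42.5%:

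| q | Observed rates | Difference (points) | Power |
|---|---|---|---|
| 0 | 57.5% vs 42.5% | 15.0 | 81.8% |
| 1% | 57.9% vs 43.1% | 14.85 | 81.0% |
| 2% | 58.4% vs 43.7% | 14.7 | 80.2% |
| 5% | 59.6% vs 45.4% | 14.25 | 77.7% |
| 10% | 61.8% vs 48.3% | 13.5 | 73.3% |

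At lower assumed rates of 40% and 25% there is more room: power is 86% at q = 0, 81% at 5% (43.0% vs 28.75%) and 75% at 10% (46.0% vs 32.5%).

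**Step 4: which marks can qualify.** Section 4.5 requires a stage I change to be pressure-related and to differ from adjacent or contralateral skin. A birthmark or plain bruise should fail that test. Residual redness from an earlier device could pass it. Stage II includes an abrasion, and its description names no comparison area. So q covers only recent pressure-type marks and abrasions that are still visible at removal.

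**The case against.** The strongest case against is that the chain is long. The mark must lie under a small area (the compress is 3.5 × 1.5 cm), be left in place by the nurse who cleans and disinfects the skin before insertion (section 4.4), persist until removal, and then be graded as a pressure lesion. Section 4.4 lists four body regions for the catheter, and nothing says a new line goes onto the skin of a failed one. At q of 1% to 2%, power in the tightest case stays above 80%. At 40% and 25%, the shift from 40% to 43% at q = 5% is under half the 95% confidence half-width of about 7 points (1.96·√(0.40 × 0.60/180) = 7.2 points). Appendices 1 to 3, including the list of data collected, appear by title only and might hold a baseline skin item.

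Most of this stands, and it limits the size of the problem. It does not close the gap. Nothing in the text shown requires the nurse to record what is seen, and if an appendix does hold such an item, neither the eligibility criteria nor the endpoint definition uses it.

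Two stronger readings are tempting. A reader might infer that every mark already present will be scored as a new ulcer; the stage I wording does not support that. A reader might also infer a bias in favour of one arm. Randomisation makes earlier marks similar in both arms on average, so the documents support dilution and inflated rates, not a directional error or a raised false-positive rate.

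**Conclusion.** The mismatch is real. The exclusion protects the puncture site, the outcome is read at the junction, no baseline reading of that skin is scheduled in the text shown, and the analysed endpoint is presence while the objective is incidence. Recent pressure-type marks and abrasions can be counted as incident ulcers.

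The size is uncertain and probably modest. It rests on an undocumented q, on assumed rates, and on the simplification that a mark present at baseline is always scored at removal; marks that resolve would make the effect smaller. In the tightest case the loss is about 1 to 2 points of power at q of 1% to 2%, 4 points at 5% and 8 to 9 points at 10%. The rise in each arm's rate, q(1 − p), bears directly on the pilot's descriptive purpose. Without a baseline record q cannot be estimated afterwards, which is the main reason to act before enrolment.

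**What to change.** 1. In section 3.3, extend the exclusion to pre-existing lesions on the skin that the catheter/extension junction is planned to cover.
2. Add one yes/no eCRF item to the D0 column in section 4.1: is that skin free of any lesion? Complete it at the eligibility check, before randomisation and so before the arm is known. A check at skin disinfection would come after randomisation, too late to affect eligibility.
3. Keep every randomised child in the intention-to-treat primary analysis (section 5.2.7). The study is open, so no entry made after randomisation by the inserting nurse should cancel an event read by the blinded assessor; that would risk replacing a non-differential error with a directional one.
4. If the site changes after randomisation, record the skin state at the new site for description only. The choice of insertion site stays with the clinical team.
5. Add a sensitivity analysis restricted to children recorded as lesion-free before randomisation.
6. Check Appendices 1 to 3 first; if a suitable item already exists, refer to it in sections 3.3 and 4.1.

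The cost is one extra eCRF field and possibly a few children not enrolled.

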4. DESIGN AND CONDUCT OF THE STUDY

4.1. STUDY SCHEDULE

- Recruitment period: 48 months
- Duration of patient participation in the study: until catheter removal.

a) Inclusion

Information and verbal consent regarding participation in the study will be obtained from the minor patient. Consent will be signed by the person(s) with parental authority (see 7.6.1: special case of the presence of only one parent).

This will be done once the medical prescription for peripheral venous access has been issued, the inclusion and exclusion criteria have been verified, and before randomisation.

The patient will be:

- either in the paediatric emergency department;
- or already hospitalised in paediatrics;

A table tracking patients to whom the study has been proposed will be kept up to date, noting the reasons for non-inclusion and refusals to participate.

b) Randomisation

Once consent to participate has been obtained, randomisation will be carried out via the computerised data base (eCRF):

- VVP placement without compress group: reference strategy group.
- VVP placement with compress group: alternative strategy group.

The peripheral venous line will then be placed according to the group designated by randomisation.

Details of the procedure for each arm are described in 4.4.

c) Follow-up

In both groups, catheter management and maintenance will be carried out by the nursing team responsible for the patient in the paediatric ward in accordance with current institutional procedures (see Appendices 1 and 2, catheter placement protocol with and without compress).

Data will be collected at the time of PPV removal. The peripheral line placed is valuable. In practice, the lines are maintained until the end of treatment unless there is redness and/or discharge at the puncture site.

When the catheter is removed, the nurse in charge of the patient removes the crepe bandage, the compress if there is one, and the catheter.

A childcare assistant from the department who has not been caring for the patient will then be called to assess the condition of the skin and report on the appearance and grade of any bedsores. The nurse will also note the presence or absence of signs of infection according to the Maddox scale. If the index is greater than 3, the paediatrician will prescribe that the catheter be sent for culture.

The microbiological analysis will be carried out by the clinical research biology team at the CHD Vendée.

d) Study design

[figure not shown]
Actions	D0 (Inclusion visit)	Every day	J Withdrawal from the VVP
Patient information	X		
Informed consent from the patient (verbal) + legal guardian (written)	X		
Randomisation	X		
Peripheral venous access	X		
Monitoring of puncture site (catheter sent for culture if local infection)		X	
Assessment of the presence of a lesion + severity of the lesion by a childcare assistant			X

4.2. GENERAL RESEARCH METHODOLOGY

The research has the following characteristics:

- ❖ Single-centre
- ❖ Open
- ❖ With blinded assessment of the primary endpoint
- ❖ Controlled
- ❖ Randomised into 2 parallel groups:
 - Placement of VVP with a compress under the catheter/tubing junction
 - Standard VVP placement, without pad under the tubing

4.3. STUDY DESIGN

4.4. DESCRIPTION OF THE INTERVENTION STUDIED

The method consists of inserting a BD Insite® catheter, gauge 20 to 24G, into a peripheral vein located in the crook of the elbow, the back of the hand, the scalp or the top of the foot.

The catheter is inserted after cleansing and disinfecting the skin with appropriate products and in accordance with the procedure in force in the department (see Appendices 1 and 2).

Once venous return has been verified, a 10 cm extension tube with a BECTON-DIC® 3-way stopcock is connected, which has been previously purged with 0.9% sodium chloride.

This catheter will be used as an access route for hydration (Polyionique®, G5% or G10% and NaCl), antibiotic therapy, analgesia, blood products or labile blood products.

Not all vein-toxic products such as chemotherapy drugs will be injected via these catheters, as they are administered via central venous lines.

[figure not shown]
We currently have 10 cm extension tubes with BECTON-DIC® three-way stopcocks. We are unable to predict future markets during our study.

There will inevitably be an extension catheter junction that will enable us to maintain our monitoring in connection with our study.

For patients with "VPP arm with compress":

A sterile non-woven compress, cut under sterile conditions (3.5 x 1.5 cm), will be inserted under the catheter-extension junction. The assembly will be held in place by a sterile, semi-permeable transparent adhesive dressing such as Tégaderm® (5 x 7 cm) or Oper film 6 x 7 cm.

This area will be secured by applying a crepe bandage (4 m x 7 cm). This will enable the childcare assistant to maintain a blind assessment of the primary endpoint.

[figure not shown]
The study will focus on the evaluation of a single catheter placed per patient.

If several catheters are placed, only the first device will be evaluated and monitored until its removal.

With regard to the duration of use, the SF2H recommendations (13) will be applied, i.e. no catheter changes will be made if good patency and asepsis are maintained until the end of treatment.

4.5. DESCRIPTION OF THE EVALUATION AND DATA COLLECTED

The primary endpoint is the development of a pressure ulcer of grade ≥ 1 on the NPUAP scale at the catheter/tubing junction.

This area is assessed several times a day by nurses, who remove the bandage without removing the fixation device (compress and transparent adhesive dressing). However, if the compress is soiled, the dressing will be changed.

NPUAP scale

The NPUAP pressure ulcer assessment scale, translated from English by ANAES, will be used. This scale allows pressure ulcers to be assessed according to four stages, graded from 1 to 4, with stage 1 being the least severe.

- Stage I: The first stage is an observable change in intact skin, related to pressure and manifested by a change in one or more of the following characteristics compared to the adjacent or contralateral body area: skin temperature (warm or cold), tissue consistency (firm or soft) and/or sensitivity (pain, itching). In people with fair skin, the pressure ulcer appears as persistent localised redness, while in people with pigmented skin, the pressure ulcer may be a persistent red, blue or purplish colour.

Example: Stage 1 pressure ulcer

- Stage II: Loss of part of the skin's thickness; this loss affects the epidermis, the dermis, or both. The pressure ulcer is superficial and clinically presents as an abrasion, blister, or shallow ulceration.

- Stage III: Loss of all skin thickness with alteration or necrosis of the subcutaneous tissue; this may extend to the fascia, but not beyond. The pressure ulcer appears clinically as a deep ulceration with or without invasion of surrounding tissues.
- Stage IV: Loss of the entire thickness of the skin with significant tissue destruction, or involvement of muscles, bones, or supporting structures (e.g., tendons, joints). Invasion and fistulas may be associated with stage IV pressure ulcers.

The catheter will be removed by the nurse in charge of the patient.

In order to allow for a blind assessment of the primary endpoint, this will be performed by a childcare assistant from the department who is on duty 24 hours a day and has not previously cared for the child. The childcare assistant will assess the pressure area and then note their observations in the patient's file (presence or absence of pressure ulcers and NPUAP grade, if applicable).

An assessment based on photographs was initially considered, but given the description of the different stages (particularly stage I, characterised by persistent redness), we believe that a direct assessment by a professional is more appropriate. Furthermore, a 2013 study concluded that assessment based on photographs is not sufficient for an accurate assessment of the stage of pressure ulcers (15).

Maddox Scale

This scale will be used to monitor for any signs of infection at the puncture site.

We have chosen not to include pain assessment as an endpoint criterion, as it is difficult to assess pain specifically related to the medical device in this population.

